## Implementation measures.

Feasibility will be measured by the percent of providers who: attend the online and in person trainings, complete role plays, attend coaching calls, and receive performance feedback. For patients, feasibility will be measured by the proportion of patients who enroll in the study, the proportion who accept proactive outreach and the proportion who complete the follow-up.

Acceptability. Qualitative interviews with 5-6 patients and 5-6 providers will be conducted at the 3-month follow-up (study 2) and 15 months post-enrollment (study 3). Interviews will be conducted by a trained research staff member. Interviews will contain open ended questions about treatment (for patients) and implementation (for providers and leaders) acceptability, burden, and suggestions for improvement. Interviews will be audio recorded. An interview guide will be submitted to the IRB prior to administering the interviews.

Effectiveness. Implementation Effectiveness will be evaluated by the proportion of patients who receive the 5As and the proportion who report using smoking cessation counseling and medication measured 3-months (study 2) or 12 months (study 3) after the start of the implementation period (assessed via patient report).

Readiness to deliver cessation treatment. This is a 25-item questionnaire measuring smoking cessation resources available to the provider, barriers to providing cessation services, cessation intervention behavior, and confidence in providing cessation treatment.

Organizational Readiness for Change. Responses to this scale reflect the extent to which the organization has the skill, training, time and resources to implement guideline consistent tobacco cessation treatment.

## 6.1 Screening and Monitoring Evaluations and Measurements

### 6.1.1 Medical Record Review

Each organization will pull a list of active patients who are English-speaking, smokers from their medical record. Case managers or providers for each patient will verify if the patient is appropriate to participate in research (without cognitive impairment, capable of providing informed consent, has a telephone and an address).

## 6.2 Efficacy Evaluations

Feasibility will be measured by the percent of providers who: attend the online and in person trainings, complete role plays, attend coaching calls, and receive performance feedback. We expect the majority (>75%) of providers and leaders to attend the trainings and receive performance feedback. For patients, feasibility will be measured by the proportion of patients who enroll in the study, the proportion who accept a proactive outreach and the proportion who complete the follow-up. Previous studies (preliminary studies 1-3) using this recruitment strategy have yielded a 30-44% response rate to the enrollment invitations, 62-71% for the proactive call, and 66-74% for follow-up assessment. Results in this range would be considered feasible.

Acceptability. Patients will complete the 8-item Client Satisfaction Questionnaire (CSQ) during the follow-up assessment. Qualitative interviews with 5-6 patients and 5-6 providers will be conducted at the 3-month follow-up (study 2), and 15 month follow-up (study 3). Interviews will be conducted by a trained research staff member. Interviews will contain open ended questions about treatment (for patients) and implementation (for providers and leaders) acceptability, burden, and suggestions for improvement.

Effectiveness. Implementation Effectiveness will be evaluated by the proportion of patients who receive the 5As and the proportion who report using smoking cessation counseling and medication measured 3-months after the start of the implementation period (study 2) and at 3, 6, and 12 months post baseline 2 (study 3) assessed via patient report. Patient Effectiveness will be measured by carbon monoxide (CO)-confirmed 7-day point-prevalence from tobacco post-intervention (3 months for study 2 and 12 months from second baseline for study 3). Secondary patient outcomes will include: 30-day point-prevalence abstinence, the number of self-reported ≥24 hour quit attempts and reductions in smoking via cigarettes per day.

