Efficacy Evaluations	Study 1: Qualitative interview, Study 2: surveys at baseline and 3 months post-implementation and qualitative interviews, Study 3: participation data, surveys at 6, 9, and 15 months post-enrollment and interviews at 15 months post-enrollment
Pharmacokinetic Evaluations	N/A
Safety Evaluations	Study 1 is only a qualitative interview. If safety concerns arise during the interview, they will be documented and submitted to the IRB.  Study 2 & 3: participants' mental health providers will be informed about their study participation. If participants note a worsening of their mental health symptoms, we will inform their providers, take appropriate clinical action if necessary, and evaluate whether this change is due to changes in their smoking, and report to the IRB as an adverse event.
Statistical And Analytic Plan	Interviews will be coded using deductive and inductive codes. We will then conduct a framework matrix analysis. We will summarize implementation data with respect to treatment delivery and utilization, and patient outcome data. For patient outcomes, we will explore the adjusted effects using a series of generalized linear mixed effects models adjusted for potential confounders, baseline values and clustering.
Data And Safety Monitoring Plan	DSMB

---

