### Patient intervention:

*Proactive outreach.* Will consist of outreach attempts with the offer of a connection to counseling.

Outreach calls. Consistent with a chronic care approach, proactive outreach will be conducted by the tobacco treatment case manager. In study 2, the case manager will make one outreach call per participant. These outreach attempts may be conducted via telephone, HIPAA secure video calls, or at an in person visit (participant preference). Each outreach attempt will include five call attempts per available telephone number. In addition, if the participant agrees to receive texts, the participant will receive up to 5 outreach text messages. If the participant is in active clinical care, the tobacco cessation case manager can also offer to see the participant in person following a regularly scheduled appointment to discuss their smoking. In study 3, the case manager will make 3 outreach attempts, each 3 months apart. The aims of the outreach are to: (1) increase motivation to stop or reduce smoking, (2) improve self-efficacy, (3) facilitate participation in evidence-based treatment. Participants will be offered mental health tailored tobacco cessation counseling delivered by the case manager or connection to local tobacco cessation programs. In addition, the case manager will discuss tobacco cessation medication options and coordinate with the participants' prescriber and case manager to facilitate receipt of medication.

Counseling. The counseling protocol is tailored to psychiatric patients. Participants will engage in up to 7 counseling sessions using a motivational interviewing style to enhance motivation and cognitive behavioral therapy skills. Counseling sessions will be timed based on the participant's readiness to quit, such that more sessions will take place surrounding quit dates. Counseling will be done by phone, secure video visit, or in person (participant preference).

*Provider intervention* will include every provider administering the 5A's at diagnostic assessment and treatment planning visits. Patients who are interested in cessation support will be referred to the tobacco treatment case manager for behavioral treatment and, if the provider can prescribe, be offered a prescription for tobacco cessation pharmacotherapy.

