Acceptability will be assessed based on the 8 item Client Satisfaction Questionnaire (CSQ) during the follow-up assessment, as well as qualitative interviews at the 12-month follow-up. Interviews will contain open ended questions about treatment (for patients) and implementation (for providers and leaders) acceptability, burden, and suggestions for improvement. The treatment will be considered acceptable if  $\geq 80\%$  of participants respond that they are at least somewhat satisfied with their participation. Average acceptability scores will be reported. Initial effectiveness will be evaluated with respect to both implementation and patient outcomes. First, we will summarize CMHC-level implementation data with respect to treatment delivery and utilization (e.g., proportion of patients receiving each of the 5A's, using smoking cessation counseling and medication) and compare across centers. Next, baseline, 3-, 6-, and 12-month patient cessation outcomes (7-day PPA and number of quit attempts), will be summarized among the aggregate sample and by CMHC. We will explore the adjusted effects using a series of generalized linear mixed effects models adjusted for potential confounders, baseline values and clustering. Models allow for flexible distribution of the outcome (binary, count) and adjust standard errors for the clustered nature of the data (clustered by provider within CMHC). Models will include a random effect for CMHC and will further adjust for potential confounders (including variables that might differ between CMHC's). Similar models can be used to test the effects on secondary outcomes (e.g., cigarettes per day) during the post-implementation period (3-, 6- and 12-months) adjusting for baseline, and to explore the effect of implementation at the patient level (use of counseling and medication) and at the provider level (SSL dose) as a predictor of primary and secondary cessation outcomes.

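### Counseling use is taken from patient report alone, leaving it unknown for survey non-responders; the case manager's session record could supply program-delivered counseling for every enrolled patient

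*Combined protocol and SAP*

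**What the plan says.** Section 6 (Implementation measures) defines implementation effectiveness partly as "the proportion who report using smoking cessation counseling and medication measured 3-months (study 2) or 12 months (study 3) after the start" of implementation, by patient report. Section 6.2 repeats the outcome but sets the Study 3 times differently: "and at 3, 6, and 12 months post baseline 2 (study 3) assessed via patient report". One section therefore has a single 12-month measure and the other has three waves.

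Section 7 gives counseling use a second role. The models may explore implementation at the patient level, meaning "use of counseling and medication) and at the provider level (SSL dose) as a predictor of primary and secondary cessation outcomes".

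On delivery, Section 5.2 (Patient intervention) says "Participants will be offered mental health tailored tobacco cessation counseling delivered by the case manager", or patients may be connected to local programs. Section 4.2.2 places the case manager on the staff of the mental health center. Section 2.1 allows up to 7 sessions per round of counseling.

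The synopsis lists, under efficacy evaluations, "Study 3: participation data, surveys at 6, 9, and 15 months post-enrollment". It does not define participation data, and Sections 6 and 7 do not link that term to counseling use.

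On response, Section 6.2 reports that earlier studies yielded "30-44% response rate to the enrollment invitations, 62-71% for the proactive call, and 66-74% for follow-up assessment" and adds "Results in this range would be considered feasible". Section 7 adopts the same ranges as feasibility criteria. It gives no method for missing survey answers.

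**The concern.** Whether a patient attended the program's counseling is something the program can know without asking the patient. Taking it only from a survey makes the measure depend on who answers. Patients in counseling are in contact with the program and may well be easier to reach at follow-up, in which case the survey rate overstates use.

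The survey item also asks only whether counseling was used. It does not ask how many sessions were attended, and no recall period is stated for it. It therefore cannot separate one session from a full course, which matters if counseling is to be studied as a predictor of cessation. At stake are a main description of how far the intervention reached patients and the exposure in the exploratory cessation models.

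**Working it through.** **Inputs.** Patients: 50 in Study 3 and 25 in Study 2 (synopsis). Follow-up completion r: 0.66 to 0.74 (Sections 6.2 and 7). The documents give no expected rate of counseling use, so p = 0.30 among responders is my assumption. So is k, the ratio of use among non-responders to use among responders.

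**1. Patients with unknown use at one assessment, N(1 - r).**
- The complement of 66-74% is 26-34%.
- Study 3: 50 × 0.26 = 13; 50 × 0.34 = 17. Observed: 37 to 33.
- Study 2, which has one follow-up: 25 × 0.26 = 6.5; 25 × 0.34 = 8.5.

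**2. Use reported at any of three waves.** If the waves were independent, the share missing all three would be 0.26³ = 1.8% to 0.34³ = 3.9%, or 1-2 of 50 patients. Missing waves usually cluster in the same patients, so the true share probably lies between this and 26-34%.

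**3. Worst-case bounds at one assessment.** The all-patient rate lies between p·r (no non-responder used counseling) and p·r + (1 - r) (all did). The width is 1 - r, whatever p is.
- r = 0.66: 0.198 to 0.538, width 34 points.
- r = 0.74: 0.222 to 0.482, width 26 points.

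**4. Excess of the survey rate, p(1 - r)(1 - k).**

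| k | r = 0.66 | r = 0.74 |
|---|---|---|
| 1 (equal use) | 0 | 0 |
| 0.5 | 0.30 × 0.34 × 0.5 = 5.1 points | 0.30 × 0.26 × 0.5 = 3.9 points |
| 0 | 0.30 × 0.34 = 10.2 points | 0.30 × 0.26 = 7.8 points |

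**5. Response gap implied by k = 0.5.** At r = 0.66, users number 33 × 0.30 = 9.9 among responders and 17 × 0.15 = 2.55 among non-responders. Response is then 9.9/12.45 = 80% in users and 23.1/37.55 = 62% in non-users. At r = 0.74 the same steps give 11.1/13.05 = 85% and 25.9/36.95 = 70%. With k = 0, every user responds.

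**6. Precision, 1.96·√(p(1 - p)/n) at p = 0.30.** The half-width is 12.7 points with n = 50, 14.8 with n = 37 and 15.6 with n = 33. The gain is only 2-3 points, so the benefit of complete records is mainly protection against non-response bias.

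**The case against.** The case for leaving the plan alone has several good parts.

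- **The survey measures something wider.** The item in Section 6 (Patient Assessments) covers counseling of any kind, and patients may be connected to outside programs. A reader might infer that session records should replace the survey, or would leave no patient's use unknown. The documents do not support that: outside counseling would stay unknown for non-responders.
- **Before-after comparison.** Section 9.1 describes a pre-post study, and Study 3 has two baselines before outreach starts. A case-manager record has no pre-outreach value, so the survey item is still needed. This stands.
- **Cessation is also self-reported.** CO testing follows only a report of abstinence. A reader might infer that session records would bring non-responders back into the exposure-cessation models. They would not: a patient without a cessation answer at a wave still has no outcome there.
- **The 66-74% range is a benchmark.** It comes from earlier studies and is a per-assessment feasibility range. Reading it as the plan's attrition assumption goes too far, and use at any wave would be missing for fewer patients. However, the Implementation measures text specifies 12 months only, and Study 2 has one follow-up, so the single-assessment figures apply there.
- **The record may already be intended.** Participation data could mean session counts, and Section 7 does not confine its utilization summary to surveys. That is possible, but the two sections that define the outcome name patient report. Conversely, no section describes a session log, so its availability is an inference. It is a modest one: feasibility already needs the proportion accepting outreach, which is not among the listed patient survey measures.
- **Little depends on it.** Counseling use has no success threshold, and the predictor analysis is exploratory. This limits the weight of the point but does not remove it.

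**Conclusion.** The point holds in limited form. Patient report is the only stated source for counseling use. At the plan's own follow-up benchmark, that leaves use unknown for 13-17 of 50 Study 3 patients at any one assessment, and fewer for use at any of three waves. For program-delivered counseling, this gap can be closed from information the program should hold.

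The excess of 4-5 or 8-10 points depends on the assumed 30% use among responders and on non-responders using counseling half as often or not at all. A reader might conclude that the survey rate is known to be biased upward. The documents give no response rates by counseling use, so the direction is plausible and the size is illustrative. With equal use in both groups there is no bias.

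I class this as a cheap improvement. It does not threaten the pilot's feasibility conclusions, because none of the feasibility criteria uses counseling use.

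**What to change.** In Sections 6.2 and 7:

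1. Define participation data as the case manager's session record for all enrolled patients: any session attended, and number of sessions.
2. Report program-delivered counseling from that record as a separate implementation outcome, with all enrolled patients as the denominator.
3. Use session count as the program-dose exposure in the Section 7 models.
4. Keep the patient-report item for counseling of any kind, outside counseling, medication and before-after comparison. State which waves count, since Sections 6 and 6.2 differ, and how missing answers are handled.
5. Compare survey response between attenders and non-attenders. The record makes this check possible and shows whether the survey rate is likely to be distorted.

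The cost is extracting session counts for 25 + 50 = 75 patients and checking that consent covers their use. The reported rate of program counseling may turn out lower than the survey would have shown. Missing cessation outcomes remain a separate problem that this change does not solve.

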## 6.3 Safety Evaluation

We will monitor adverse events if they are reported by the patient. The study does not provide any medications or devices, so we expect there to be few adverse events reported by patients.

# 7 STATISTICAL CONSIDERATIONS

Qualitative analysis. Using a structured debriefing form, post-interviews notes will be written at the end of each interview and reviewed by all co-investigators. Interviews will be transcribed and deidentified. Transcription will be completed by Landmark Associates Inc. We will develop analytical codes using an iterative method in which interview notes are reviewed to: 1) consider whether the qualitative agenda is appropriate and complete, and 2) develop an initial coding structure. Deductive codes will be drawn from the interview questions (e.g., treatment needs); review of the interview notes will also allow the creation of inductive codes which capture emergent concepts from the interviews. Investigators and trained study staff will code the transcripts. Each transcript will be independently coded by two coders, who will meet to resolve discrepancies. Final codes will be entered into NVivo qualitative data analysis software. We will conduct a framework matrix analysis to identify the most effective ways to organize the content and logistics of implementation strategy and pilot study design and will help guide our pilot study protocol.

Quantitative Analysis. As a preliminary step, CMHC, provider, and patient-level characteristics will be summarized at baseline. Differences between CMHC's will be tested using graphical methods, non-parametric, and parametric tests as appropriate (e.g., Wilcoxon rank-sum test for skewed data, t-tests for normally distributed continuous data & chi-squared tests for categorical data). Consistent with Aim 3, feasibility and acceptability will be assessed as follows: feasibility will be measured by the percent of providers who attend the online and in person trainings, complete role plays, and receive performance feedback. Implementation will be considered feasible if at least 75% of providers and leaders attend the trainings and receive

performance feedback. For patients, feasibility will be measured by the proportion of patients who enroll in the study, the proportion who accept a proactive outreach and the proportion who complete the follow-up. The study will be considered feasible if results are in the range of those found in preliminary studies: 30-44% response rate to the enrollment invitations, 62-71% for the proactive call, and 66-74% for follow-up assessment (See Preliminary Studies Section).

Acceptability will be assessed based on the 8 item Client Satisfaction Questionnaire (CSQ) during the follow-up assessment, as well as qualitative interviews at the 12-month follow-up. Interviews will contain open ended questions about treatment (for patients) and implementation (for providers and leaders) acceptability, burden, and suggestions for improvement. The treatment will be considered acceptable if  $\geq 80\%$  of participants respond that they are at least somewhat satisfied with their participation. Average acceptability scores will be reported. Initial effectiveness will be evaluated with respect to both implementation and patient outcomes. First, we will summarize CMHC-level implementation data with respect to treatment delivery and utilization (e.g., proportion of patients receiving each of the 5A's, using smoking cessation counseling and medication) and compare across centers. Next, baseline, 3-, 6-, and 12-month patient cessation outcomes (7-day PPA and number of quit attempts), will be summarized among the aggregate sample and by CMHC. We will explore the adjusted effects using a series of generalized linear mixed effects models adjusted for potential confounders, baseline values and clustering. Models allow for flexible distribution of the outcome (binary, count) and adjust standard errors for the clustered nature of the data (clustered by provider within CMHC). Models will include a random effect for CMHC and will further adjust for potential confounders (including variables that might differ between CMHC's). Similar models can be used to test the effects on secondary outcomes (e.g., cigarettes per day) during the post-implementation period (3-, 6- and 12-months) adjusting for baseline, and to explore the effect of implementation at the patient level (use of counseling and medication) and at the provider level (SSL dose) as a predictor of primary and secondary cessation outcomes.

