## PROTOCOL SYNOPSIS

Study Title	Proactive Outreach for Smoking Treatment (POST)
Funder	NIH/NIDA
Clinical Phase	N/A
Study Rationale	
The US Public Health Service (USPHS) designated tobacco dependence as a chronic disease. This is especially true for smokers with serious mental illness (SMI) who make more cessation attempts and are less successful sustaining long-term abstinence than the general population. There is a significant health disparity wherein individuals with SMI have a higher tobacco use prevalence and a greater risk for tobacco-related mortality than the general population. Chronic care models suggest chronic disease management requires a multidisciplinary care team to assess tobacco use, administer treatment, support patient self-management, and monitor progress. Proactive telephone outreach to smokers and brief provider interventions are two effective chronic disease management strategies. Community based mental health centers (CMHCs) are a primary treatment access point for many smokers with SMI. However, rates of intervention with smoking by CMHC providers are low. In order to implement the chronic care model for tobacco dependence for CMHCs, comprehensive implementation strategies are needed.

Study Objective(s)	
Primary
 
 
• To develop an implementation strategy to implement proactive tobacco cessation treatment into community mental health treatment settings
 
 
Secondary
 
 
• To test the effectiveness of the implementation strategy as well as the effectiveness of a proactive tobacco cessation treatment strategy.
 

Test Article(s) (If Applicable)	The study intervention combines provider intervention about tobacco (asking patients if they use tobacco, advising patients to quit, assessing willingness to quit, assisting with quitting via counseling or medication or referral for treatment, and arranging for follow-up), and proactive outreach (calling smokers in the health system and offering treatment).
Study Design	There are 3 studies proposed in the grant. The first study consists of qualitative interviews of leadership, clinical staff, and patients at two community mental health centers. The following two studies

---

	will be two sequential pilot tests of the implementation strategy in two community mental health centers.

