##### 4.1.2 Study Intervention

Study 1: There is no intervention. This is a qualitative study only.

Study 2: The organization will participate in an implementation intervention, 6 months in duration, that consists of an in-person, hands-on training workshop, performance feedback based on anonymous patient surveys and/or electronic mental record data, and coaching calls. Organizational leaders will also participate in a series of planning meetings. Study staff will work with site leadership to develop templated language for documentation of the 5 A's in the electronic health record. Providers will be given handouts on smoking cessation resources, smoking cessation medications, and a tool to help guide them through the 5 A's. The workshop will cover the importance on intervening with people with serious mental illness about smoking in mental health treatment

settings, available treatments, documentation, and how to do the 5 As. We will make arrangements for lunch to be provided during the workshop.

The patient intervention will consist of providers discussing tobacco with patients during their visits using the “5 A’s” to ask the patient about their tobacco use, advise tobacco users to quit, assess readiness to quit, assist patient in quitting by providing counseling, medication, or a referral, and arranging for follow-up. In addition, 25 patients who consented to the study will receive outreach to discuss their tobacco use and offer to help them obtain smoking cessation medication through their existing providers and also to provide ongoing counseling (up to 7 counseling sessions by phone, secure video, or in person). Outreach may also be done in person in the context of routine clinical care if the participant prefers it.

Study 3: The organizational intervention is the same as in study 2, except the implementation support will last for 9 months, and leaders will participate in a sustainment meeting at the end of the implementation to form a plan to sustain the intervention once implementation support is removed.

The patient intervention is the same except that 50 patients will receive 3 outreach attempts, over 9 months, each with an invitation to help the patient connect with treatment.

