#### **4.3.2 Total Number of Study Sites/Total Number of Subjects Projected**

Study 1: Study procedures will be conducted by Hennepin Healthcare Research Institute staff, but will recruit from 2 community mental health centers (Central Minnesota Mental Health Center and Lee Carlson Center).

Study 2: Study procedures will be conducted by Hennepin Healthcare Research Institute staff and two staff members from Lee Carlson Center.

Study 3: Study procedures will be conducted by Hennepin Healthcare Research Institute staff and two staff members from Central Minnesota Mental Health Center.

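### Section 7 plans to compare implementation and treatment use across centers, but each pilot appears to run at one center, so center cannot be separated from study version

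*Combined protocol and SAP*

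**What the plan says.** The Quantitative Analysis part of Section 7 describes center-level summaries of 5A's receipt and treatment use, ending "using smoking cessation counseling and medication) and compare across centers". It names no time point, no test and no estimate for that comparison, and it has no term for study.

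Section 4.3.2 allocates the sites. For Study 2: "Study procedures will be conducted by Hennepin Healthcare Research Institute staff and two staff members from Lee Carlson Center". For Study 3: "Study procedures will be conducted by Hennepin Healthcare Research Institute staff and two staff members from Central Minnesota Mental Health Center". Only Study 1, the interview study, is said to recruit from both centers. The synopsis says the second and third studies "will be two sequential pilot tests of the implementation strategy in two community mental health centers".

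The two pilots differ by design:

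- **Outreach.** Section 5.2: "In study 2, the case manager will make one outreach call per participant". Section 4.1.2, on Study 3: "The patient intervention is the same except that 50 patients will receive 3 outreach attempts, over 9 months".
- **Implementation support.** Section 5.2 gives 3 months for Study 2 and 9 for Study 3. Section 4.1.2 gives 6 and 9.
- **Reading time of 5A's receipt and treatment use.** Section 6 (Implementation measures) sets 3 months for Study 2 and 12 months for Study 3. Section 6.2 adds 3- and 6-month readings in Study 3.

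**The concern.** A comparison across centers is naturally read as a statement about settings: one center delivered more of the 5A's, or its patients used more counseling and medication. Here the second center also has two more rounds of outreach, longer support, a later calendar period and, if Section 6 is followed, a reading nine months later. Any of these could raise cumulative treatment use with no difference between the centers. Nothing in Section 7 warns the reader of this. The planned adjustment for variables that differ between centers cannot help, because study version does not vary within a center.

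**Working it through.** The plan gives no figure for this comparison, so there is nothing to reproduce. The check is whether a center effect can be identified.

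**1. Design coding.** Let c = 0 for Lee Carlson (Study 2, 25 patients) and c = 1 for Central Minnesota (Study 3, 50 patients). The patient numbers come from the synopsis. Every design feature is then a linear function of c:

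- study = c
- outreach rounds = 1 + 2c
- support in months = 3 + 6c (Section 5.2) or 6 + 3c (Section 4.1.2)
- reading time in months = 3 + 9c (Section 6)

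A matrix with columns for intercept, center, study, rounds, support and reading time has 6 columns and rank 2, whichever support length is used for Study 2. One between-group contrast is available, and it carries all five labels.

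**2. Shared 3-month point only.** Study 3 also has a 3-month reading (Section 6.2), and its second outreach falls due only at 3 months after the second baseline (Section 4.2.3). Rounds and reading time then largely coincide between the studies. With columns for intercept, center and study, the rank is 2 of 3: center is still aliased with study.

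**3. All time points.** Take Study 2 at 3 months (1 round) and Study 3 at 3, 6 and 12 months (1, 2 and 3 rounds). With columns for intercept, center, study, rounds and time, the rank is 4 of 5. Rounds and time separate from center; study does not.

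**4. Study 3 alone.** Center is constant, so its column equals the intercept and there is no contrast.

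**5. Illustration of size.** Assume identical centers and the same acceptance probability p in each round. Ever accepting is p after one round and 1 − (1 − p)³ after three independent rounds. The values 10%, 20% and 30% are assumptions. The documents' only related figure is the 62-71% response to the proactive call in preliminary studies (Sections 6.2 and 7).

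| p per round | 1 round | 3 independent rounds | Gap (points) |
|---|---|---|---|
| 0.10 | 10% | 1 − 0.90³ = 27% | 17 |
| 0.20 | 20% | 1 − 0.80³ = 49% | 29 |
| 0.30 | 30% | 1 − 0.70³ = 66% | 36 |
| 0.62 | 62% | 1 − 0.38³ = 95% | 33 |
| 0.71 | 71% | 1 − 0.29³ = 98% | 27 |

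Correlation between rounds shrinks the gap. With a latent correlation of 0.5, p = 0.30 gives 53% after three rounds, a gap of 23 points, and p = 0.10 gives 22%, a gap of 12 points.

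The table concerns acceptance of outreach, not the outcomes that Section 7 compares. Providers deliver the 5A's at visits, so extra outreach rounds do not multiply 5A's receipt in this way.

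**The case against.** Five arguments can be made in the plan's defense.

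1. **No outcome test is planned.** This is right. A reader might infer from the sentence that differences between centers "will be tested using graphical methods, non-parametric, and parametric tests as appropriate" that the implementation outcomes will be tested too. In context that sentence belongs to the preliminary summary of baseline characteristics, which outreach rounds and follow-up length cannot affect. It also helps to show which variables differ between centers. Those tests are not at fault here. The aliasing of the outcome comparison does not depend on a test.

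2. **Section 7 may cover Study 3 only.** It refers to Aim 3 and uses 3-, 6- and 12-month outcomes, which are Study 3 features. On that reading nothing is confounded, but there is no second center, so the phrase cannot be carried out.

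3. **One center per pilot is an inference.** For Studies 2 and 3, Section 4.3.2 says whose staff conduct the procedures, and eligibility refers to either of the two sites. That is fair as far as it goes. Still, Section 4.3.2 is the only text that allocates centers to pilots, and the synopsis and eligibility wording are compatible with it.

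4. **A 3-month comparison would remove much of the difference.** It would largely remove the round count and reading time. Section 7 does not specify it, and calendar period and any other change between the pilots would remain.

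5. **No conclusion hangs on it.** No aim compares centers, and the feasibility and acceptability criteria do not use a center contrast. This stands and limits the weight of the point.

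**Conclusion.** The point holds for the outcome comparison in Section 7. If both pilots are pooled, center and study version are one variable and no covariate adjustment can separate them. If only Study 3 is meant, the comparison does not exist. Neither reading gives an interpretable result. The conclusion rests on Section 4.3.2 meaning one center per pilot.

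Three stronger readings are not supported:

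- **That the artifact has a known size.** The documents give no uptake rate for this setting, and the figures above describe ever accepting outreach under assumed rates. They are not estimates for the 5A's or for use of counseling and medication.
- **That the plan would declare a false significant difference between centers.** It specifies no test of these outcomes, so an error rate would belong to a procedure the plan does not contain.
- **That the comparison would decide which setting implements better.** Nothing in the aims or success criteria gives it that role.

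This is a minor-to-moderate point in an exploratory pilot, worth correcting because the correction costs so little.

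**What to change.** In Section 7, delete the cross-center comparison of implementation and treatment-use data and report Study 2 and Study 3 separately. State which studies the section covers.

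If a side-by-side display is wanted, restrict it to the 3-month assessment, the one reading time both studies share. Label it descriptive, and state that center cannot be separated from study version or calendar period.

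The baseline tests between centers need not be deleted. Sections 4.1.2 and 5.2 should also be reconciled on the length of implementation support in Study 2 (6 v 3 months), so that any description of how the pilots differ is accurate.

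The cost is wording only: no change to data collection, sample size or success criteria. What is given up is a comparison that could not be interpreted.
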